COMIRB Protocol

COLORADO MULTIPLE INSTITUTIONAL REVIEW BOARD
[name] [contact] [contact]

Protocol #: 21-2580

Project Title: Comparison of Exercise Mode on Disruptions in Calcium Homeostasis

Principal Investigator: [name]

Version Date: 03/25/2021

I. Hypotheses and Specific Aims:

This study will fill a knowledge gap regarding how endurance exercise mode may differentially impact the bone biomarker response to exercise in older Veterans. Endurance exercise is a first-line strategy to prevent or manage cardiometabolic diseases but can lead to bone loss under certain conditions. The data generated will be used to develop a future clinical trial investigating exercise and lifestyle strategies that minimize both the risk of cardiometabolic diseases and osteoporosis.

SA1: Determine the effect of *exercise mode* on the serum ionized calcium (**iCa**; secondary), parathyroid hormone (**PTH**; secondary), c-telopeptide of type I collagen (**CTX**; **primary**), and procollagen of type-1 n-terminal propeptide (**P1NP**; secondary) responses to exercise in older adults. 30 older adults (15 women, 15 men, aged 60+ years) will each perform two, 60-minute exercise bouts: 1) high-intensity (70-80% heart rate maximum (**HRmax**)) cycling exercise (weight-supported); and 2) high-intensity (70-80% **HRmax**) treadmill exercise (weight bearing).

H1a: Cycling exercise (weight supported) will result in a greater increase in bone resorption compared to treadmill exercise (weight bearing).

H1b: Treadmill exercise (weight bearing) will result in a greater increase in P1NP at the 24-hour time point compared to cycling exercise (weight supported).

SA2 (exploratory): Determine if men and women have a differential bone biomarker response to same exercise. This aim will be achieved by comparing the **iCa**, **PTH**, **CTX**, and **P1NP** response from each exercise bout between sexes. This will generate preliminary data to determine if exercise needs to be tailored by sex.

II. Background and Significance:

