differences observed.²² However, our preliminary data and the evidence presented in Figure 2 cannot rule out the possibility that mode of exercise is an important contributing factor. Without knowing how mode of exercise contributes to the difference in bone biomarkers, information is lacking about what types of exercise may be the most beneficial to bone. To be able to appropriately prescribe exercise for health and to maintain or improve quality of life, we must fully understand the positive and potential negative effects of the mode of

exercise on bone turnover. The proposed research is the first step in determining how exercise mode may need to be tailored to Veteran needs, especially older Veterans using exercise to reduce the risk of diabetes, cardiovascular disease, and/or osteoporosis, but may have orthopedic limitations that impair the ability to perform weight-bearing exercise.

IV. Research Methods

A. Outcome Measure(s): Change in iCa, PTH, CTX, and procollagen of type 1 n-terminal propeptide (P1NP; a marker of bone formation)

B. Description of Population to be Enrolled:

Participants. Healthy older (60+ y) women and men who are accustomed to regular exercise lasting approximately 1 hour in duration will be eligible to participate. All volunteers must be accustomed to performing 60 minutes of vigorous cycling and treadmill exercise.

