Participants will arrive between 0900h and 1000h. After vital signs are obtained, an intravenous catheter for blood sampling will be positioned in a forearm vein. Participants will remain rested in a semi-recumbent position for ~15 minutes; a blood sample will be obtained at the end of this interval. After voiding, body weight (in hospital gown) will be measured and, after dressing, participants will move to the cycle ergometer or treadmill and remain seated or standing for 5 minutes before exercise. A second pre-exercise blood sample will be obtained immediately before exercise. This sampling paradigm will enable us to address the contention that positional changes have not been adequately considered in evaluating the changes in plasma volume in response to cycling and running.³⁶ Participants will be allowed deionized water *ad libitum* during exercise and recovery. Water consumption and urine volumes will be recorded for calculation of plasma volume changes. They will return between 1000h and 1100h the next morning after a 10- to 12-h fast for the 24-h blood sample.

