Blood collections (Fig 4) and assays. For each of the exercise tests, two pre-exercise blood samples will be obtained as described in the preceding paragraph. Blood samples (10 mL each) will be obtained after 15, 30, 45, and 60 minutes (exercise), and at 75, 90, 120, and 300 minutes during recovery, and 24 hours after the end of exercise. An additional blood sample 48 hours after exercise will be available as an optional procedure for analysis of iCa, P1NP, and CTX. After exercise, participants will remain in a semi-recumbent position for the duration of recovery. Blood samples will be processed by the CTRC Core Laboratory (partial off-site waiver will be pursued) and stored at -80°C. Samples from all exercise sessions for an individual will be analyzed in batch to minimize batch effects. The exceptions to this will be the parameters measured in real time (hematocrit (**HCT**), iCa, pH) during the study visits by the iSTAT analyzer (Abbot Point of Care, Princeton, NJ). Serum (or plasma) assays will include: **1)** PTH by immulite two-site enzyme immunoassay (Siemens, Erlangen, Germany; CTRC Core Lab), **2)** CTX by chemiluminescence (Immunodiagnostic Systems, Boldon Business Park, UK; CTRC Core Lab), **3)** P1NP by chemiluminescence (Immunodiagnostic Systems; CTRC Core Lab), and **4)** tCa by indirect ion-selective electrode (Beckman Coulter Inc; UCH Clinical Lab). Laboratories where assays will be conducted are CAP and CLIA certified. Laboratory-specific intra- and inter-assay coefficients of variations are generally lower than those determined by the manufacturers. PTH, CTX, iCa, and tCa, concentrations during and after exercise will be adjusted for shifts in plasma volume as previously described.⁸ These outcomes cannot be assayed in a VA laboratory due to the lack of the necessary combined analysis system. Performing each assay individually in a wet lab would double the blood required, increasing participant burden and risk.

Feasibility measures. Participants will be asked to rate multiple aspects of their experience, including preference for each mode of exercise, ease of getting to and from the exercise facility, and their likelihood of participating in a center-based exercise program that would require multiple trips to the VA facility several times per week over multiple months. This information will be used to inform future intervention designs.

[figure not shown]

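### P1NP is left out of the plasma-volume adjustment, so a plasma-volume change that differs by exercise mode could enter the P1NP contrast; its size is unknown

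*Combined protocol and SAP*

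**What the plan says.** Section IV.C (Blood collections and assays) lists four serum or plasma assays: PTH, CTX, P1NP and tCa. The P1NP entry reads "P1NP by chemiluminescence (Immunodiagnostic Systems; CTRC Core Lab". The same paragraph then states: "PTH, CTX, iCa, and tCa, concentrations during and after exercise will be adjusted for shifts in plasma volume as previously described". P1NP is the only one of the four assays not in that sentence.

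Section I names P1NP as a secondary outcome and gives it its own hypothesis, H1b, that treadmill exercise "will result in a greater increase in P1NP at the 24-hour time point compared to cycling exercise". Section IV.A describes P1NP as "a marker of bone formation".

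Section IV.C (Submaximal exercise sessions) takes two pre-exercise samples. The first follows about 15 minutes of semi-recumbent rest. Before the second, "participants will move to the cycle ergometer or treadmill and remain seated or standing for 5 minutes before exercise". The stated reason for this sampling is the contention that "positional changes have not been adequately considered in evaluating the changes in plasma volume in response to cycling and running". Water intake and urine volume are recorded so that plasma-volume change can be calculated. Haematocrit is one of the real-time measurements, in a list that ends "iCa, pH) during the study visits by the iSTAT analyzer".

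Section IV.F repeats the CTX analysis for iCa, tCa and PTH. P1NP is missing from that list too.

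**The concern.** P1NP is measured as a concentration. If the circulating amount stays the same and plasma volume falls, the measured value rises; if plasma volume expands, it falls. The protocol accepts this for CTX and the calcium-related analytes, and treats plasma volume in cycling versus running as a live issue. Yet the one marker of bone formation is left out of the correction without a reason.

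What is at stake is the P1NP comparison between modes. A difference in plasma-volume change could be read as a difference in bone formation, or could hide one. Because Section IV.F is also silent on P1NP, nothing in the analysis text fills the gap.

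**Working it through.** **No plan figure to reproduce.** The only power statement (30 subjects, at least 80% power, 0.12 ng/mL) concerns CTX. The documents give no expected P1NP effect, no P1NP standard deviation and no plasma-volume change by mode. All sizes below therefore rest on assumed inputs.

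**Step 1: haematocrit to plasma volume.** Assume a starting haematocrit of 42% and constant red-cell volume. The protocol defers its own method to a cited paper, so this formula is also an assumption.

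Change in plasma volume = (Hct1/Hct2) × ((100 − Hct2)/(100 − Hct1)) − 1

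- 42 to 41: (42/41) × (59/58) − 1 = +4.2%
- 42 to 43: (42/43) × (57/58) − 1 = −4.0%
- 42 to 40: (42/40) × (60/58) − 1 = +8.6%
- 42 to 44: (42/44) × (56/58) − 1 = −7.8%

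**Step 2: plasma volume to unadjusted P1NP.** With the circulating amount unchanged, the concentration changes by 1/(1 + plasma-volume change) − 1.

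- 42 to 41: 1/1.0421 − 1 = −4.0%
- 42 to 43: 1/0.9599 − 1 = +4.2%

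If haematocrit moves by one point in one mode and not in the other, the unadjusted contrast shifts by about 4% of the P1NP level. Two points shift it by about 8%. If both modes shift equally, the contrast shifts by 0.

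**Step 3: when this can reach a P1NP contrast.**

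- *Exercise and early recovery:* directly, for any mode difference in plasma-volume change at those samples.
- *24 hours, by persistence:* only if a mode difference in plasma volume lasts until the next morning.
- *24 hours, through the baseline:* only if the second pre-exercise sample is the baseline. Section IV.C does not say which of the two is used.

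Illustration of the baseline route: assume plasma volume is 5% lower at the standing treadmill baseline than at the seated cycling baseline, and equal in both modes at 24 hours. Set the true level at 100.

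- Cycling: 100 at baseline, 100 at 24 hours, change 0%.
- Treadmill: 100/0.95 = 105.3 at baseline, 100 at 24 hours, change 100/105.3 − 1 = −5.0%.
- After adjustment to the same baseline sample: plasma volume has risen by 1/0.95 − 1 = 5.3%, so the treadmill 24-hour value becomes 100 × 1.053 = 105.3, change 0%.

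If the semi-recumbent sample is the baseline, posture is the same in both modes and this route closes.

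**Step 4: what a gap could do to a test.** Take a paired t-test with n = 30, two-sided 0.05 (sidedness is not stated in the plan), no true effect, and plasma volume lower in one mode only. The probability of p ≤ 0.05 is:

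| Plasma-volume gap | Spurious P1NP difference | SD of paired difference 10% of baseline | 15% | 20% |
|---|---|---|---|---|
| 1% | 1.0% | 0.08 | 0.07 | 0.06 |
| 2% | 2.0% | 0.19 | 0.11 | 0.08 |
| 5% | 5.3% | 0.80 | 0.46 | 0.29 |
| 10% | 11.1% | 1.00 | 0.98 | 0.84 |

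The result runs from negligible to serious over inputs that the documents do not narrow.

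**The case against.** The strongest reply is that H1b is read at 24 hours, whereas the protocol's plasma-volume material concerns acute events: posture before exercise, and the response to exercise itself. The 24-hour draw follows a 10- to 12-hour fast, in the same morning window for both modes. No document shows a mode-dependent plasma-volume difference at that time. This stands, and it limits the 24-hour concern to the two conditional routes above.

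A reader might infer more in three places, and the documents do not support it.

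- *That unstated posture at the 24-hour draw biases H1b.* It is unstated for both modes, in the same people, with randomized and counterbalanced order. That adds noise. It gives no bias unless posture differs systematically by mode.
- *That P1NP and CTX would be on different scales in a comparison of formation with resorption.* Section IV.F plans no ratio or joint analysis, and H1a and H1b are separate hypotheses. Nor do the documents say explicitly how the adjustment, which is defined by a cited method, applies at 24 hours even for CTX.
- *That the sponsor has decided to analyse P1NP unadjusted.* P1NP is missing from both the adjustment sentence and the secondary-outcome list, which looks as much like a drafting slip as a choice.

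It is also fair to say that adjustment is not free of error. By Step 1, a one-point haematocrit reading error moves an adjusted value by about 4%. If there is no true shift at 24 hours, adjusting only adds noise there.

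What survives is that the text, followed literally, leaves P1NP uncorrected without a reason. A slip still needs correcting.

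**Conclusion.** The omission is certain. Its consequence is conditional. A plasma-volume change that differs by mode would bias the unadjusted P1NP contrasts during exercise and early recovery. It would bias the 24-hour contrast only by persisting until then or by entering through a baseline sample taken in different postures. The figure of about 4% per haematocrit point illustrates scale from an assumed 42%; it does not estimate the bias in this trial. Direction is equally unknown: in the baseline illustration the error runs against H1b, and the opposite assumption would reverse it.

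It would be too strong to say that H1b is biased as planned, because no document shows a plasma-volume difference between modes at 24 hours. The CTX primary analysis is unaffected. Severity is low to moderate. Confidence is high for the omission and low for the size of any bias.

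**What to change.** - Add P1NP to the adjustment sentence in Section IV.C, with the same method as CTX.
- Name the pre-exercise reference sample and use the same one for P1NP and CTX. The semi-recumbent sample is preferable, because its posture is the same in both modes.
- Add P1NP to the secondary-outcome list in Section IV.F.
- Report unadjusted P1NP alongside as a sensitivity result.
- Apply the adjustment at 24 hours, and at the optional 48-hour draw, where haematocrit is available. The protocol should say whether it is measured at those draws; it says only that haematocrit is measured during study visits.
- If leaving P1NP unadjusted is deliberate, state the reason instead.

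The cost is a few words in two sections and one derived variable, using haematocrit that is already collected at study visits. The statistical price is some added noise in adjusted 24-hour values from haematocrit measurement error; the unadjusted result makes that visible.

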most effectively stimulate bone formation (i.e., anabolic factors).⁶ Potential *metabolic responses* to exercise that influence the extent to which exercise stimulates bone resorption (i.e., catabolic factors) have received less attention. Our research has focused on the disruption of Ca homeostasis during exercise as the trigger for a metabolic cascade that activates bone resorption.^{3,7-11} The working model in our previous research (Fig 1) hypothesized that sweating during exercise leads to dermal Ca loss and a decline in iCa. This triggers an increase in parathyroid hormone (PTH), which stimulates bone resorption to mobilize Ca from bone and stabilize serum Ca. From this research, we have generated unequivocal evidence that 1) vigorous exercise causes a decline in serum ionized Ca (iCa) concentration;^{9,11-13} 2) the decline in serum iCa during exercise is the major determinant of the subsequent increases in PTH and bone resorption (as reflected by c-telopeptide of type I collagen; CTX);⁹ 3) the increases in PTH and CTX are robust and occur after only 15 minutes of exercise;^{9,12,13} and 4) despite the fact that serum PTH returns to the pre-exercise level by 1 h after exercise, bone resorption remains activated at least 4 hours.⁹ We also generated evidence that, in contrast to our hypothesis, dermal Ca loss through sweating is *not* the major cause of the decrease in serum iCa or increases in PTH and CTX during exercise.^{12,13} Other factors regulate this response. Possible factors include changes in metabolic acidosis^{14,15} or serum phosphate.¹⁶

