The effects of treadmill versus cycling exercise on the change in CTX will be evaluated using linear contrasts in a repeated measures maximum likelihood model with all available data. We have utilized this approach in similar experiments,^{9,37,38} and it is conceptually identical to repeated measures analysis of variance but avoids the deletion of cases with missing assessments. Estimates are unbiased under the assumption that missing data are missing at random. Linear contrasts will be used to estimate within-condition changes and between-condition differences in changes over the 60-minute exercise bouts and the recovery periods separately. Primary comparisons will include up to the 24-hour blood draw. Secondary analyses will be conducted utilizing the 48-hour timepoint, but results will be interpreted with caution due to the potential for low sample size. This analysis will be repeated for secondary outcomes (change in iCa, tCa, PTH). The distributions of the outcome measures will be checked. If there are severe departures from a normal distribution, transformations (e.g., natural logarithm) will be applied as appropriate to achieve an endpoint that is approximately normally distributed. To minimize missing data, all participants will be informed of the importance of complete follow-up and encouraged to complete the study per the protocol. Although statistical methods can be used to adjust for missing data, these methods rely on the untestable assumption that data are either **1)** missing completely at random, for which no adjustment is needed, or **2)** missing at random, for which the effect of the “missingness” can be removed through statistical modeling. We will instead focus on preventing missed exercise tests and samples. Due to the mechanistic nature of the studies and the use of the results to guide decisions about a future randomized controlled trial, no adjustments for multiple comparisons will be performed. All analyses will be conducted using SAS software version 9.4 M4 (SAS Institute Inc, Cary, NC, USA) and a p-value ≤ 0.05 defining statistical significance. For the exploratory analyses in SA2, we will use the same statistical approach as SA1 while including sex in the maximum likelihood model. Results will be interpreted with caution due to the low sample size, and will be used to generate hypotheses for future research.

G. Summarize Knowledge to be Gained:

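### Only plasma-volume-adjusted ionized calcium is described, so a cycling-versus-treadmill difference in iCa could not be told apart from a difference in fluid shift

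*Combined protocol and SAP*

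**What the plan says.** Section IV.C (Blood collections and assays) states: "PTH, CTX, iCa, and tCa, concentrations during and after exercise will be adjusted for shifts in plasma volume as previously described". The method is given only by citation (reference 8). The same paragraph says that iCa and haematocrit are read in real time on a point-of-care analyser, so measured iCa values will exist.

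Section IV.F (Data Analysis Plan) applies the CTX model to the changes in iCa, tCa and PTH. On the contrasts it says: "Linear contrasts will be used to estimate within-condition changes and between-condition differences in changes over the 60-minute exercise bouts and the recovery periods separately". It does not say whether adjusted or measured values enter the model, and it describes no unadjusted or sensitivity analysis.

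Section II (Background and Significance) states the working model in terms of concentration: "vigorous exercise causes a decline in serum ionized Ca (iCa) concentration", which then drives PTH and bone resorption.

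Section IV.C (Submaximal exercise sessions) provides two pre-exercise samples. The first follows about 15 minutes semi-recumbent. For the second, "participants will move to the cycle ergometer or treadmill and remain seated or standing for 5 minutes before exercise". The stated purpose is: "This sampling paradigm will enable us to address the contention that positional changes have not been adequately considered in evaluating the changes in plasma volume". The section adds: "Water consumption and urine volumes will be recorded for calculation of plasma volume changes". It does not say which of the two samples is the reference for the plasma-volume change.

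**The concern.** Adjusted iCa and measured iCa are different quantities. The measured value is the concentration that the working model treats as the trigger for PTH. The adjusted value is that concentration rescaled by the estimated change in plasma volume. When plasma volume moves, one can change while the other does not.

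The plan itself gives reasons why the shift might differ by mode. Posture before exercise depends on the equipment, water is taken freely, and recovery is semi-recumbent after both modes. If the on-equipment sample is the reference, the recovery shift is counted from a different starting posture in each session.

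At stake is the meaning of the iCa contrast. A mode difference in adjusted iCa would naturally be read as a difference in calcium homeostasis, when it might be wholly or partly a difference in haemoconcentration. With p ≤ 0.05 and no multiplicity adjustment (section IV.F), such a result would be declared significant.

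**Working it through.** **Inputs from the documents.** 30 subjects, each performing both modes; p ≤ 0.05; a CTX difference of 0.12 ng/mL with at least 80% power.

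**Inputs assumed, because the documents do not give them.** The correction formula; resting iCa (1.20 to 1.25 mmol/L, with 1.22 or 1.25 used below); the plasma-volume change v; its gap between modes; the SD of the within-person iCa difference; the CTX level (0.3 to 0.7 ng/mL).

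**1. The plan's own figure.** The only power statement concerns CTX. For a paired comparison, two-sided, by normal approximation, it implies an SD of the within-person difference of 0.12 × √30 / (1.960 + 0.842) = 0.235 ng/mL (0.227 by noncentral t). The plan states no SD, so the figure can be neither confirmed nor refuted. Nothing below depends on it.

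**2. Apparent fall within a mode.** Take adjusted = measured × (1 + v) with measured iCa constant. The apparent change is then baseline × v.
- 3% contraction: 1.20 × 0.03 = 0.036 mmol/L fall.
- 12% contraction: 1.25 × 0.12 = 0.150 mmol/L fall.
- 5% expansion: 1.25 × 0.05 = 0.0625 mmol/L rise, so the sign follows the shift.

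**3. Apparent difference between modes.** With measured iCa the same in both modes, the difference is baseline × (gap in v).
- 1-point gap: 1.22 × 0.01 = 0.012 mmol/L.
- 5-point gap: 1.22 × 0.05 = 0.061 mmol/L.
- Equal shifts: 0.
- Equal shifts with a real measured difference: it is only rescaled. At v = −10%, 0.020 becomes 0.9 × 0.020 = 0.018 mmol/L.

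**4. The opposite case.** Let a fraction f of the plasma-volume loss concentrate iCa passively, so measured = 1.25 × (1 + f × (1/(1 + v) − 1)). The adjusted change is then 1.25 × v × (1 − f). At v = −10%:

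| f | Measured change (mmol/L) | Adjusted change (mmol/L) |
|---|---|---|
| 0 | 0 | −0.125 |
| 0.5 | +0.069 | −0.0625 |
| 1 | +0.139 | 0 |

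With f = 1 and shifts of −10% and −5%, measured iCa is 1.3889 and 1.3158. That is a mode difference of 0.073 mmol/L in the unadjusted values and none in the adjusted ones. The distortion has moved to the other version.

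**5. Chance of a significant mode contrast in adjusted iCa when measured iCa does not differ.** Paired t test, N = 30, two-sided 0.05 (assumed, as the plan does not state sidedness), baseline 1.25 mmol/L.

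| SD of within-person difference (mmol/L) | Equal shifts | 2-point gap (0.025) | 5-point gap (0.0625) |
|---|---|---|---|
| 0.03 | 5% | 99% | 100% |
| 0.05 | 5% | 75% | 100% |
| 0.08 | 5% | 38% | 98% |
| 0.10 | 5% | 26% | 91% |

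**6. Effect on CTX.** The same 1-to-5-point gap moves the adjusted contrast by between 0.3 × 0.01 = 0.003 and 0.7 × 0.05 = 0.035 ng/mL. That is 0.003/0.12 = 2.5% to 0.035/0.12 = 29% of the target difference. The upper end needs the highest assumed CTX level and the largest assumed gap together.

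**The case against.** The strongest defence has four parts.

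- **Adjustment is a legitimate choice.** For a constituent concentrated by fluid loss, it removes haemoconcentration, and the raw value is then the misleading one (step 4). Which version should lead depends on whether the target is circulating concentration or net calcium movement. This stands: the documents do not settle how far iCa concentrates passively, so they do not show that adjusting is an error or that measured iCa should replace it.
- **The plan already attends to posture.** It takes two pre-exercise samples for that purpose and records haematocrit, water intake and urine. This also stands. What is missing is the analysis step: no reference sample is named, and no plasma-volume comparison by mode is planned.
- **Silence is not exclusion.** Nothing forbids reporting measured iCa. That is true, but a version added after the results are seen is open to selection.
- **The stakes are limited.** iCa is secondary, the study is a mechanistic pilot, and PTH is measured alongside as a check. This bears on priority, not on whether the gap exists.

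A reader might infer that adjustment manufactures an iCa fall and a mode difference whenever plasma volume shifts. The documents do not support that. A fall needs contraction without proportionate concentration, a spurious mode difference needs unequal shifts, and no section states that the shifts will be unequal.

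**Conclusion.** The gap is real but bounded. The plan adjusts iCa and describes no analysis of measured iCa, while its working model is about the circulating concentration. Unequal plasma-volume shifts could then give an iCa mode contrast with no difference in measured iCa: 0.012 to 0.061 mmol/L for a gap of 1 to 5 points, and zero for equal shifts. The size rests on the assumed formula, on iCa of about 1.22 mmol/L, on the assumed gap, and on measured iCa staying constant. It shrinks to nothing if iCa concentrates in full proportion to the fluid loss. Because the unadjusted values then carry the mirror-image distortion, both versions are needed.

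A reader might also infer that the primary CTX conclusion is compromised. The documents do not show this. Adjusted CTX can remain primary, and its exposure is smaller and depends on assumptions.

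**What to change.** Add to section IV.F, before results are seen:

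1. The iCa mode contrast is estimated twice with the same model, as measured and plasma-volume adjusted. A mode difference is interpreted as a change in circulating iCa only if it appears in the measured values.
2. Unadjusted CTX and PTH mode contrasts are sensitivity analyses. Adjusted CTX remains primary.
3. Plasma-volume change is reported by mode and time point, with the semi-recumbent pre-exercise sample as the common reference, since that posture is the same in both sessions.
4. The correction formula is written out rather than only cited.

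**Cost.** A short addition to the analysis plan and one rerun of the same model on data already being collected, with no new samples or visits. The downside is that two versions of each contrast must be reported, and they may disagree. If they do, the plasma-volume change by mode helps the reader see why.
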